# **11.7. Study Drug Accountability**

An accurate and current accounting of the dispensing and return of study drug for each subject will be maintained on an ongoing basis by a member of the study site staff. The number of study drug dispensed will be recorded on the Investigational Drug Accountability Record. The study monitor will verify these documents throughout the course of the study.

## **12. SAFETY ASSESSMENT**

## **12.1. Medical History**

A complete medical history will be obtained at the Screening Visit including the recording of demographic data (date of birth, sex, age, race, ethnicity), collection of previous surgeries, medications and chronic conditions, past or present illnesses or dysfunctions, substance/drug abuse, and history of allergies or idiosyncratic responses to drugs.

## **12.2.** Physical Examination

A complete physical examination including body weight will be completed for all subjects at Screening, at End-of-Treatment or Early Termination, and at the Follow-Up visits. The complete physical examination will include a review of the subject's general appearance, skin, head and neck (eyes, ears, nose, mouth, and throat), lymph nodes, thyroid, musculoskeletal/extremities, cardiovascular system, lungs, abdomen and a brief examination of the neurological system.

Height will be recorded in centimeters (cm) with the subject's shoes removed. Body weight will be measured in kilograms (kg); subjects will remain in their normal clothing with shoes and jacket (and/or outer clothing) removed.

## 12.3. Columbia-Suicide Severity Rating Scale (C-SSRS)

The Columbia Suicide Severity Rating Scale (C-SSRS) is a brief questionnaire that provides for the identification, quantification and standardized assessment of the occurrences and severity of suicidal ideation and behavior (see http://cssrs.columbia.edu) (Posner 2011). The typical administration time is a few minutes. The "Baseline Version" of the C-SSRS will be assessed at Screening. The C-SSRS "Since Last Visit" version will be assessed at Day -1, Day 36, Day 72, Day 109, and Early Termination.

#### 12.4. Vital Signs

Vital sign measurements will be obtained after the subject has been seated for 3 minutes. Vital signs will include sitting blood pressure (systolic and diastolic measurements), pulse rate (beats per minute), respiratory rate (breaths per minute), and oral temperature. In order to ensure accuracy, out-of-range vital signs may be repeated once, at least 2 minutes after an abnormal finding.

Vital signs will be collected at prior to the first dose/application and weekly thereafter. Temperature checks may be permitted daily.

#### 12.5. 12-Lead Electrocardiogram

A 12-lead electrocardiogram (ECG) will be obtained after the subject has been in a supine position for a minimum of 3 minutes. Abnormal ECGs may be repeated for confirmation in which case only

the repeated ECG will be recorded. The QT interval corrected for heart rate will be calculated with Fridericia's formula (QTcF).

ECGs will be obtained at Screening, Day -1, ET and EOS visit.

## **12.6.** Clinical Laboratory Measurements

All clinical laboratory samples will be sent to a local laboratory for analysis. Up to approximately 40 mL of blood will be collected for clinical chemistries, hematology, and pregnancy test (if applicable) from each subject during the study. During the Screening Period, Clinical Laboratory Measurements may be repeated at the discretion of the Investigator.

The Clinical Laboratory evaluations will consist of the following:

- Total Hematology as well as differential and Coagulation: red blood cell count, white blood cell count with differential (neutrophils, lymphocytes, monocytes, eosinophils, basophils), hemoglobin, hematocrit and platelets, Prothrombin Time (PT) and Partial Thromboplastin Time (PTT).
- Serum Chemistry: aspartate aminotransferase (AST), alanine aminotransferase (ALT), albumin, alkaline phosphatase, bicarbonate, total bilirubin, blood urea nitrogen, phosphorus (inorganic) calcium, chloride, creatine phosphokinase, creatinine, gamma glutamyl transferase, glucose, lactate dehydrogenase, potassium, sodium, total protein, and uric acid.
- Urinalysis: microanalysis for specific gravity, pH, protein, glucose, ketones, blood, nitrites, leukocytes. If positive for blood, protein or nitrites, a microscopic examination will be performed.
- Serology: hepatitis B surface antigen, hepatitis C antibody and human immunodeficiency virus antibody.
- Pregnancy Tests: will be performed for all female subjects. A serum β-hCG pregnancy test will be performed at Screening. A urine pregnancy test will be performed at check-in, Day 36, Day 72, Day 109, and the Early Termination visit,. A positive pregnancy test will exclude a subject from enrollment into the study. A positive urine pregnancy test will be confirmed with a serum β-hCG pregnancy test.
- Urine Screen for Alcohol, Drugs of Abuse: Urine samples will be tested for alcohol, drugs of abuse (amphetamines, methamphetamines, benzodiazepines, barbiturates, cannabinoids, cocaine, and opioids) at Screening and at check-in of the Treatment Phase. If the test is positive for any of the tested analytes the subject will be excluded from further study participation.

• Laboratory safety tests will be obtained at the Screening visit, Day -1, Day 36, Day 72, Day 109, and at the Early Termination visit. In addition, laboratory safety tests may be performed at various unscheduled time points if deemed necessary by the investigator.

# 12.7. COVID-19 Testing

Subjects must have a negative COVID-19 viral test at Screening and Day -1 in order to be eligible for enrollment. COVID-19 testing will be performed weekly while subjects are housed in the clinic. Other reasons for testing could include but are not limited to:

- If a subject displays COVID-19 symptoms (fever, cough, loss of taste or smell, or diarrhea).
- If any subject is suspected of coming in contact with a confirmed COVID-19 positive person.
- At the discretion of the Principle Investigator/in consultation with the Medical Monitor.

A detailed site COVID-19 Continuity Plan could be provided to include guidance for testing frequency and related safety precautions.

#### 12.8. Adverse Event Assessments

Adverse events (AEs) shall be monitored continuously from the administration of the first dose of study drug until either the Follow-Up or Early Termination visits as noted on the Schedule of Events. AEs will be monitored continuously and solicited using a non-leading question immediately after dosing and at 1, 3, 5, 10, 24 hours post-dose, after all other procedures at each specified time are performed. Definitions and details of AE reporting and documentation are listed in **Section 19**.

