In each period wherein the treatment consists of a patch, the subjects will wear a total of 5 patches for a total of 35 days (5 weeks). The last (5th) patch in the period will be removed after the morning blood draw on Day 36 (168-hour time point after the last patch in the period). No treatment will be administered on Day 36 of the period; additional post-wear PK blood samples will be collected on Day 36 after any patch treatment. Because of the lag time of donepezil plasma concentrations after TDS application, the  $C_{max}$  and  $T_{max}$  values at steady state. in some subjects, may be observed after removal of the TDS (past 168 hours after TDS application). This is the reason why an additional day (Day 36 in each treatment period) was added to the PK sampling schedule, after TDS removal at the end of the TDS dosing interval (168 hours).

In each period (Period 2 or 3) wherein the treatment consists of oral Aricept®, the subjects will an oral dose daily for a total of 35 days (5 weeks). The last oral dose in the period will be administered on the morning of Day 35. No treatment will be administered on Day 36 of the period; a PK blood sample will be collected in the morning of Day 36 at 24 hours after the last oral dose.

In Period 1, all subjects will wear patches (Treatment A). In Periods 2 and 3, subjects will either wear patches (Treatment B) or receive once-per-day oral Aricept® (Treatment C).

- The treatment in Period 2 will start on the morning of Study Day 37 after the predose blood draw for Period 2 is collected. No treatment will be administered on Study Day 72. For the patch treatment in Period 2, the patch will be removed on Study Day 72 after the 168-hour blood sample collection.
- The treatment in Period 3 will start on the morning of Study Day 73 after the predose blood draw for Period 3 is collected. No treatment will be administered on Study Day 108. For the patch treatment in Period 3, the patch will be removed on Study Day 108 after the 168-hour blood sample collection.
- Follow-Up Visit: 5 ±2 days after the day of the last oral drug administration or last TDS removal during the Treatment Phase, subjects will enter a Follow-Up Visit to evaluate safety parameters.

There will be no washout phase between treatment periods (with the exception of Day 36 within each period to collect post-treatment PK blood samples).

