#### 9.4.2. Procedures on In-Clinic Days Period 2 & 3 Treatment B & C

The following assessments will be performed during the in-clinic days of Periods 2 &3:

- 1. Blood samples for pharmacokinetics will be collected at times listed in Section 14.1.
- TDS Adhesion Assessments will be performed at times listed in Section 15.0 Treatment B only. A photograph of the TDS will be taken at adhesion timepoints listed in Section 15.0 Treatment B only
- 3. Review of concomitant medications, treatment and/or therapies
- Assessment of adverse events. While subjects are in the research clinic, AEs will be monitored continuously and solicited using a non-leading question at times listed in Section 13.8. The inquiry using non-leading questions will be performed after all other procedures are conducted for the specified time points.

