# 9.4.4. Procedures for Drug Administration Treatment C (Period 2 & 3)

The following assessments will be performed for drug administration for during Period 2 & 3):

- 1. Subjects will receive a light meal approximately 30 minutes prior to drug administration.
- 2. Vital signs after a minimum of 3 minutes of rest (respiratory rate, pulse rate, blood pressure, oral temperature) will be collected at times listed in **Section 13.4**.
- 3. Blood samples for pharmacokinetics will be collected at times listed in Section 14.1.
- 4. Randomized subjects will receive 10 mg Aricept® donepezil (1 x 10 mg/day tablet) administered QD for 35 consecutive days during either Period 2 or Period 3. Study drug will be given orally and be administered with approximately 240 mL of water. Subjects will be instructed not to crush, split, or chew the study drug tablets.
- 5. Water will be allowed ad libitum up to 1 hour prior to dose administration. No water maybe consumed for 1-hour prior through 1 hour after dosing (except for water needed to administer study drug). After 1 hour following dose administration, subjects may drink water ad libitum.
- 6. Review of concomitant medications, treatment and/or therapies.
- Assessment of adverse events. While subjects are in the research clinic, AEs will be monitored continuously and solicited using a non-leading question at times listed in Section 13.8. The inquiry using non-leading questions will be performed after all other procedures are conducted for the specified time points.

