6.11.1 Adverse Events

A treatment emergent adverse event (TEAE) is defined as:

- Any AE that has a new onset during the study between the initiation of study drug and the follow-up visit.
- Any pre-existing AE that has worsened in severity on or after the initiation of study drug till the follow-up visit.

The following rules will be used to assign a TEAE to a treatment:

- A TEAE will be assigned to the treatment received immediately before onset.
- Any TEAE reported within Period 1, Day 36, when no treatment is administered, will be attributed to the last treatment received before Day 36 began.
- If the severity of a TEAE increases in a later period the TEAE at the increased severity also will be assigned to the treatment received immediately before the increase in severity.

Page 33 of 61 Confidential

All TEAEs are defined as being definitely, probably, possibly related or unrelated to the study drug. If an AE has missing relationship it is assumed to be definitely related to the study drug for analysis purposes. Additionally, any SAE considered definitely, probably, or possibly related to the study drug will also be classified by the Sponsor as either "expected" or "unexpected" upon review by the medical monitor.

Adverse event severity will be graded as Grade 1: Mild, Grade 2: Moderate, or Grade 3: Severe or Medically Significant but not immediately life-threatening. Maximum severity will be assumed for an AE with missing severity.

All AEs will be coded using the most current version of the Medical Dictionary for Regulatory Activities (MedDRA version 23.1, updated to include activities related to COVID-19) by SOC and PT.

The following tables will be presented for AEs by treatment and overall using the Safety Population:

- Overall incidence and the number of AEs, SAEs, TEAEs leading to withdrawal.
- TEAE by system organ class and preferred term, incidence and number of events
- Treatment related TEAE by system organ class and preferred term, incidence and number of events
- Serious TEAE by system organ class and preferred term, incidence and number of events and "expected or unexpected" classification
- TEAE by system organ class and preferred term by nearest relationship to study drug, incidence and number of events
- TEAE by system organ class, preferred term and maximum severity, incidence
- TEAEs leading to early withdrawal by system organ class and preferred term, incidence

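### AE questioning times are defined only relative to dosing, which gives oral Aricept about six to seven times as many defined prompts as the TDS and can tilt the by-treatment TEAE tables

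*Protocol*

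**What the plan says.** Protocol 12.8 (Adverse Event Assessments) sets the questioning rule: "AEs will be monitored continuously and solicited using a non-leading question immediately after dosing and at 1, 3, 5, 10, 24 hours post-dose". It also requires continuous monitoring for everyone: "Adverse events (AEs) shall be monitored continuously from the administration of the first dose of study drug until either the Follow-Up or Early Termination visits".

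Dosing frequency differs between the treatments. Under 9.4.4, Aricept is "administered QD for 35 consecutive days during either Period 2 or Period 3". Under 6.1, a patch period consists of five patches, each worn for seven days. Section 8.1 makes Study Days 36, 72 and 108 drug-free.

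On other days, 9.4.2 (in-clinic days, Treatments B and C) states: "AEs will be monitored continuously and solicited using a non-leading question at times listed in Section 13.8". Section 9.3.3 (Period 1 in-clinic days) and the removal-day lists in 9.4 and 9.4.3 use the same instruction. The cross-reference is out by one: in the current numbering the section meant is 12.8. None of these lists adds times of its own.

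Section 18.1.2 adds AE probing at each subject visit. For reporting, Protocol 17.6 summarises TEAEs by treatment, and SAP 6.11.1 says "The following tables will be presented for AEs by treatment and overall". Neither document adjusts for how often subjects were asked. The study is open-label (Protocol 8.3).

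**The concern.** Asking more often tends to find more mild, transient events. If the schedule in 12.8 is followed as written, one treatment is questioned every day and the other two mainly around weekly patch changes. The treatments then sit side by side in the same TEAE tables.

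Two things are at stake. The safety objective (Protocol 5.3) is the tolerability of the once-weekly TDS, and the TDS is the product with few defined prompts, so its own AE profile may be under-recorded even if nobody compares it with Aricept. The comparison will be made anyway: Protocol 2.2 gives possibly fewer gastrointestinal effects as a reason for the patch, and Section 3 already contrasts TDS and Aricept events across studies. In an open-label trial, spontaneous reporting cannot be assumed equal between treatments, so it does not automatically even out unequal questioning.

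**Working it through.** The documents state no number of AE prompts, so there is no planned figure to reproduce. The counts below follow from the text.

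**Inputs.** Six prompt times per dosing event, at 0, 1, 3, 5, 10 and 24 h (Protocol 12.8). 35 oral doses per period (9.4.4). Five TDS applications per period, 168 h apart (6.1).

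**Prompts per period, read literally.**
- Treatment C: 35 × 6 = 210. The 24 h prompt of one dose falls at about the same time as the immediate prompt of the next. Merging them leaves five distinct times per dose plus the last 24 h prompt: 35 × 5 + 1 = 176.
- Treatment A or B: 5 × 6 = 30. Nothing merges, because the 24 h prompt is six days before the next application.
- Ratio: 210/30 = 7.0, or 176/30 = 5.9.

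**Time covered by defined prompts.**
- Oral: 35 × 24 = 840 h of 840 h.
- TDS: 5 × 24 = 120 h of 5 × 168 = 840 h, or 14.3%.

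**Longest gap between defined prompts.**
- Oral: 24 − 10 = 14 h.
- TDS: 168 − 24 = 144 h in each patch week.
- After patch 5 no new patch goes on at 168 h. In Periods 1 and 2 the next dose-linked prompt comes when the following treatment starts, at 192 h. In Period 3 no further dose follows. Sections 9.4 and 9.4.3 list questioning on Days 36, 72 and 108, but a post-dose time has no meaning on a day without a dose.

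**What the imbalance could do (illustration only).** Assume equal true event rates, onsets spread evenly over 35 days, every event captured in prompted time, and a share s captured outside it. With f = 5/35 = 1/7, the observed TDS-to-oral ratio of event counts is f + (1 − f) × s:

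| s (assumed) | Observed TDS/oral ratio |
|---|---|
| 0.5 | 0.57 |
| 0.7 | 0.74 |
| 0.9 | 0.91 |
| 1.0 | 1.00 |

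In terms of the share found only on asking (1 − s), the apparent reduction is (1 − s) × 6/7: 0.2 × 6/7 = 17% and 0.5 × 6/7 = 43%. No document gives s. These are upper bounds for the assumed shares, because the formula treats an uncaptured event as lost for good.

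**The case against.** The best defence is that the protocol does not confine questioning of TDS subjects to the first 24 h. Sections 9.3.3, 9.4, 9.4.2 and 9.4.3 require solicited questioning on in-clinic and removal days, including the drug-free ones. The natural reading is that questioning was intended throughout and the times were left undefined. This stands as to intent. It does not supply a schedule: each section points to times that do not exist on a day without a dose, so a site may ask at a time of its choosing or not at all.

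Other ascertainment is substantial. Subjects are confined, monitoring is continuous, and investigators probe at visits. TDS subjects have 14 adhesion checks per patch, or 70 per period (Protocol 14). Monitoring and probing do reduce under-capture. Adhesion checks, however, are contacts and not AE questions.

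A reader might infer that TDS questioning misses peak exposure, since 6.1 says "Because of the lag time of donepezil plasma concentrations after TDS application" the maximum may come after 168 h in some subjects. The documents do not support that for patches 1 to 4: the prompts after the next application fall 168 to 192 h after the previous one, which is when such a late peak would occur. Only after patch 5 is there no dose-linked prompt at that point.

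A reader might also take the 17 to 43% as an estimate of bias. It is not. The share is assumed, a question at the next application can bring out earlier events, and SAP 6.11.1 counts a subject once per preferred term, so incidence does not scale with the number of prompts.

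Finally, the AE tables are descriptive, the safety objective names no comparison with Aricept, and no pharmacokinetic conclusion depends on them. That is correct and limits the weight of the point.

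**Conclusion.** The concern holds as a risk created by a stated rule. The only defined prompts are dose-linked. Followed literally, they give 176 to 210 prompts in an oral period against 30 in a TDS period, roughly 6:1 to 7:1, with 144 h of each patch week lacking a defined prompt. The sections that call for questioning on the intervening days do not cure this, because they borrow the same times.

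The likely direction of an effect from this schedule is fewer recorded events on the TDS, which would favour it in the by-treatment TEAE tables and understate its own event profile. The documents do not show that such bias will occur, and its size is unknown. It depends on how many events surface only on asking and on what sites do on non-dosing days. The change should be made, but the primary bioequivalence conclusion is untouched.

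**What to change.** In Protocol 12.8, set one solicitation schedule at the same clock times on every in-clinic day, including Days 36, 72 and 108, for all three treatments. Align 9.3.3, 9.4, 9.4.2 and 9.4.3 to it and correct their cross-reference. Existing contacts can carry it: daily dosing for oral subjects and the 12-hourly adhesion checks for TDS subjects.

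Keep all TEAEs in the main tables. Leaving events out according to how they were elicited would drop genuine TEAEs, and neither document plans to record how each one was elicited.

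The SAP addendum is headed as post database lock, so conduct may already be complete. In that case, report the questioning schedule actually used, state unequal solicitation as a limitation of the by-treatment TEAE tables, and add a sensitivity table limited to onsets within 24 h of dosing on period Days 1, 8, 15, 22 and 29. In those windows all three treatments share the same six prompts. The table will hold fewer events, and onset dates recalled after a long gap may be less exact on the TDS.

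The cost is protocol wording and the site's query schedule, or one extra table and a limitation statement after the fact. The downside is that more mild TDS events may be recorded.

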#### **13. PHARMACOKINETIC ASSESSMENTS**

#### 13.1. Pharmacokinetic Plasma Sample Collection

Pharmacokinetic Sampling for Treatments A and B (TDS application):

The blood PK samples will be collected at the nominal time points listed below  $\pm 5$  minutes for the first 24 hours and 10 minutes thereafter.

The following blood PK samples will be collected in 2 mL EDTA K2 lavender top tubes:

- Week 1 (Days 1 to 7): Pre-TDS #1 application (Day 1), and at 2, 6, 12, 24, 48, 72, 96, 120, and 144 h after TDS #1 application.
- Week 2 (Days 8 to 14): Pre-TDS #2 application (Day 8 at 168 h after TDS #1 application), and at 24, 48, 72, 96, 120, and 144 h after TDS #2 application.
- Week 3 (Day 15 to 21): Pre-TDS #3 application (Day 15 at 168 h after TDS #2 application).
- Week 4 (Day 22 to 28): Pre-TDS #4 application (Day 22 at 168 h after TDS #3

application).

The following blood PK samples will be collected in 4 mL EDTA K2 lavender top tubes:

- Week 5 (Day 29 to 35): Pre-TDS #5 application (Day 29 at 168 h after TDS #4 application), and at 3, 6, 12, 24, 36, 48, 60, 72, 84, 96, 108, 120, 132, 144, and 156 h after TDS #5 application
- Week 6 (Day 36): Pre-TDS #5 removal (Day 36 at 168 h after TDS #5 application), and at 2, 6, 8, 10, and 12 h after TDS #5 removal.

The 168-h post-dose PK blood samples will be collected before removal of the worn TDS.

# Pharmacokinetic Sampling for Treatment C (oral dosing):

The blood PK samples will be collected at the nominal time points listed below  $\pm 5$  minutes for the first 24 hours and 10 minutes thereafter.

The following blood PK samples will be collected in 2 mL EDTA K2 lavender top tubes:

- Week 1, Day 1: Pre-Dose, and at 1, 2, 3, 4, 6, 8, 12 and 24 h after oral administration (before Day 2 oral administration)
- Week 2: Day 8 Pre-Dose
- Week 3: Day 15 Pre-Dose
- Week 4: Day 22 Pre-Dose

The following blood PK samples will be collected in 4 mL EDTA K2 lavender top tubes:

- Week 5: Day 29 Pre-Dose
- Week 5: Day 35 Pre-Dose, and 1, 2, 3, 4, 6, 8, 12 and 24 h after oral administration (the 24-h sample will be collected on Day 36.

One hundred and four (104) blood samples will be collected during the entire treatment period. A total of approximately 316 mL blood per subject will be drawn for PK analysis.

Detailed instructions for the collection, processing, storage and shipment of the plasma PK samples will be included in the Laboratory Manual. The date and time of collection of each PK sample will be recorded.

